- Sample Size Determination:
  - From the more recent preliminary data analysis, 83.3% (20/24, 95% CI: 62.6%-95.2%) of patients had success based on symptoms and feeding methods in the innovative strategy group, while only 35% (7/20, 95% CI: 15.4%-59.2%) had success in the standard therapy group. In order to provide greater assurance than afforded by comparing to historical control of the standard therapy, a total of evaluable 100 patients will be randomized into the innovative feeding strategy or standard therapy group. The chi- square test yields 80% power to detect 27% or higher increase in proportion of success while maintaining an overall one-sided  $\alpha$  level of 0.025. This conservative power calculation is supported by the preliminary data and assumes the proportion of success for the standard therapy is around 40% and a group-sequential design with O’Brien-Fleming error spending function.
- Interim Analysis:

- One interim futility analysis will be undertaken at about 50% information prior to the final analysis at 100% information, corresponding to 50 and 100 evaluable patients, respectively. The boundary is determined using Lan-DeMets spending functions to simulate O'Brien-Fleming boundaries with an overall one-sided  $\alpha$  level of 0.025. Using the target proportion of success, the boundary at the futility analysis expressed as a p-value is 0.297. We plan to enroll 120 patients to allow for 20% of attrition.
- Intention to treat analysis:

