  - Every patient who had been randomized will be included in the analysis. If a patient drops off before end of study and no symptom score has been measured, we will treat the patient as a failure. Beside the intention to treat analysis, we will also perform the analysis with only those patients that complete the study. Linear mixed models will be used to study the associations between the primary endpoints for Aim 1 (symptom scores) and treatment, and trend across time. The interaction term “group x time” will be included in the model to study whether the two treatment groups have different “behavior” across time. Confounder variables, such as medications, feeding position or volume, will be included in the models. Logistic regression models will be used to assess success of the treatment vs. standard of care. Also, potential confounders (e.g. feeding method: oral vs. tube) will be included and studied in these models. Holm's method will be used to adjust for multiple comparisons. All the secondary variables listed above, will be analyzed using either linear mixed models or logistic regression models. Model goodness of fit tests and residual analyses will be performed to assess the models. Interaction terms and potential confounder variables will be included.
  - The proposed projects will focus on esophageal provoking stimuli in designing multi-faceted innovative therapies, that will be studied in a prospective single center randomized blinded controlled trial. The pH- Impedance data with associated symptom indices will be analyzed. This trial will advance our knowledge of GER and GERD in infants. These studies will likely mandate the development of infant-specific diagnostic and treatment paradigms to manage not only GERD but also other diseases where GERD is a co-morbidity.

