- Overall Study Endpoints: Primary clinical outcome occurs at time 2 study or at discharge if time 2 study not completed. Secondary study outcomes occur at time 2 studies. Secondary clinical outcome measures (growth characteristics, development and long term feeding outcomes) will be collected up to 24 months.
- Methods to overcome potential confounders: Data will be collected from EPIC documentation, feeding diaries, parent interviews and follow up appointments. While inpatient, these are documented regularly. After discharge, we will be dependent on parents to provide the data.
- Removal and management of subject(s) from protocol: The investigator and/or the parent(s) have the right to withdraw from study at any time and opt for the standard of care. Parent(s) that withdraw their infants from the study therapy will be encouraged to continue to remain in the study for all follow up evaluations. Those who choose completely withdrawal from the study will be encouraged to follow the standard of care; wherein, response failures are followed for secondary outcomes until 18 months.
- Secondary Outcome Measures: (up to 24 months, for Bayleys developmental score) Secondary outcome measures (growth characteristics, development and long term feeding outcomes) will be collected up to 12 months.

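### Enrolling 120 covers 16.7% attrition, not the stated 20% (which leaves 96 evaluable, not 100), and no power is given for the intention-to-treat analysis

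*Combined protocol and SAP*

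**What the plan says.** All the planning figures are in section 3.3 of the protocol. Under Sample Size Determination, "a total of evaluable 100 patients will be randomized into the innovative feeding strategy or standard therapy group", and the chi-"square test yields 80% power to detect 27% or higher increase in proportion of success" at an overall one-sided level of 0.025, assuming about 40% success on standard therapy. The Interim Analysis paragraph places the futility look and the final analysis at half and full information, "corresponding to 50 and 100 evaluable patients, respectively", with a futility boundary of p = 0.297. The same paragraph ends: "We plan to enroll 120 patients to allow for 20% of attrition". The figure of 120 also stands in sections 1.0 and 11.0.

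The Intention to treat paragraph then defines two analysis sets. For the first, "Every patient who had been randomized will be included in the analysis", with the rule "If a patient drops off before end of study and no symptom score has been measured, we will treat the patient as a failure". For the second, "we will also perform the analysis with only those patients that complete the study". Section 6.1 adds that "Primary clinical outcome occurs at time 2 study or at discharge if time 2 study not completed". The report's Statistical Methods section confirms that the primary outcome was analysed by intention to treat.

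**The concern.** There are two linked points.

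First, attrition is lost from those enrolled. Read that way, the enrolment figure does not deliver the evaluable number it is meant to protect.

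Second, the 80% is attached to 100 evaluable patients. The intention-to-treat analysis has a different denominator (all randomised) and a rule that turns some missing outcomes into failures. With equal loss, such a rule lowers both success rates in proportion and so narrows the 27-point difference, while the larger denominator works the other way. The plan states no power for this analysis. Nor does it say whether 40% and 67% are success rates among evaluable infants or among all those randomised, and the answer depends on that.

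What is at stake is whether the stated planning figures are right and which analysis the 80% belongs to.

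**Working it through.** **Inputs.** From section 3.3: 100 evaluable, 120 enrolled, 20% attrition, control success 40%, difference 27 points (so 67% in the study arm), one-sided alpha 0.025, futility boundary 0.297. From section 6.1: 1:1 allocation. Assumptions made here: the 0.297 is a one-sided p-value, the look is at half the patients, and the final critical value is 1.96.

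**Method.** Exact power: sum the binomial probabilities of all pairs of success counts for which the pooled chi-square z is at least 1.96. The figure with the look also requires a one-sided p of at most 0.297 at the half-way look.

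**1. The plan's own 80%.** 50 per arm, 0.40 versus 0.67: 79.8% fixed, 78.4% with the look. The stated 80% therefore reproduces, as power for 100 evaluable patients without the futility look. The pooled normal formula gives 78.1%.

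**2. The attrition allowance.**
- 120 × (1 − 0.20) = 96 evaluable, not 100.
- Loss at which 120 still leaves 100: 20/120 = 16.7%.
- Enrolment that leaves 100 after 20% loss: 100/(1 − 0.20) = 125.
- 100 × 1.20 = 120, so the 20% was evidently applied to the evaluable number.

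**3. Power at 96 evaluable.** 48 per arm: 77.0% fixed, 75.7% with the look. The fall from 100 is 79.8 − 77.0 = 2.8 points by exact calculation, or 78.1 − 76.4 = 1.7 points by the pooled formula.

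**4. Intention-to-treat power, 120 randomised (60 per arm).** If 40% and 67% are rates among evaluable infants and a share d of each arm is imputed as failure, the rates become 0.40(1 − d) and 0.67(1 − d), and the difference 0.27(1 − d). The look is placed at 30 per arm.

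| Share imputed, d | Rates compared | Difference | Power, fixed / with look |
|---|---|---|---|
| 5% | 38.0% v 63.7% | 25.7 points | 82% / 80% |
| 10% | 36.0% v 60.3% | 24.3 points | 78% / 75% |
| 20% | 32.0% v 53.6% | 21.6 points | 68% / 66% |

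If 40% and 67% already describe all randomised infants, nothing is diluted, and 60 per arm gives 86% / 84%. Placing the look at 25 per arm, as the 50-patient interim would imply, lowers the second figure by only 0.2 to 0.5 points.

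**5. How attrition relates to d.** The two are not the same. The failure rule needs a missing symptom score, and section 6.1 takes the primary outcome at discharge when the Time 2 study is not done. So d may be well below the attrition rate, and the 20% row is the pessimistic end for equal loss at the plan's own figure.

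**The case against.** The strongest reply is that the headline gap hardly touches the primary analysis. By intention to treat, all 120 would enter the test; the 96 matters only for the additional completer analysis, where it costs 3 points at most. One can also read the sentence loosely as 20 extra infants per 100 evaluable. The first part stands and limits the weight of the point. The second explains where 120 came from, but does not make it an allowance for 20% attrition.

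It is also fair to say that 80% may well hold for the intention-to-treat analysis. At 5% imputed failures, or if the rates describe all randomised infants, it is met. A reader might infer that the 80% is false for that analysis; the documents support only that its power is unstated and conditional.

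A reader might further infer that loss differed by arm and cut power more sharply. The documents give no planned unequal loss. The failure rule turns on missing scores, and Table 2 of the report has score changes for 31 of 36 conventional and 34 of 40 study infants, so 5 (13.9%) and 6 (15.0%) have none. That is an upper bound on imputed failures, because an infant not yet on full oral feeds can succeed by feeding alone, and it is nearly balanced.

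Lastly, the report's Statistical Methods section speaks of enrolling 100 and omits the 120. One might infer that it dropped the evaluable basis. It did not: its next sentence refers to evaluable patients, and so does its limitations paragraph.

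**Conclusion.** The allowance is misstated: 120 enrolled covers 16.7% loss, and 20% loss leaves 96 evaluable with about 77% power (76% with the look) instead of 79.8% (78.4%). The stated 80% is sound for 100 evaluable patients. Power for the intention-to-treat analysis is missing from the plan. Under equal loss and evaluable-patient rates it runs from about 82% / 80% at 5% imputed failures to 68% / 66% at 20%; under all-randomised rates it is about 86% / 84%. These figures rest on the stated 40% and 67%, 120 randomised 1:1, and a one-sided reading of the 0.297 boundary.

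It would be tempting to conclude that the trial was planned too small. The documents do not support that. The 27-point target is conservative against the pilot gap of 83.3% − 35% = 48.3 points, and accrual ended at 76 with the funding, so neither 120 nor 125 came into play. This is a minor correction to planning figures.

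**What to change.** In section 3.3:

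- Restate the allowance as 16.7%, or keep 20% and state 96 evaluable with about 77% / 76% power (fixed / with look).
- Label the 80% as power for 100 evaluable patients.
- Say whether 40% and 67% are success rates among evaluable or among all randomised infants.
- Give intention-to-treat power by share imputed as failure (about 82% / 80% at 5%, 78% / 75% at 10%, 68% / 66% at 20%, or about 86% / 84% if the rates are for all randomised), stated as conditional on equal loss, with a note that unequal loss by arm would change it.

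Optionally, bring the report's Statistical Methods wording on enrolling 100 into line with 100 evaluable and 120 enrolled. The cost is a few sentences and a slightly less favourable stated figure. No extra enrolment and no change to the analysis are needed.

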### **3.4 Scientific or scholarly background for, rationale for, and significance of the research based on the existing literature and how will it add to existing knowledge**

- This proposal is a logical extension of our current R01 and is built on Novel Concepts, and State-Of-The-Art Methods. Previously we have developed, validated, and safely used the approaches and equipment necessary to assess GER and GERD in infants including: a) novel multimodal esophageal sensory-motor testing using manometry provocation methods, b) respiratory inductance plethysmography, c) ultrasonography of glottal motion, d) video-manometry, e) pH-Impedance with direct observation/video correlation of symptoms, and f) robust analytical and statistical paradigms. We are translating these methods to improve outcomes in infants with feeding problems, e.g., improving successful feeding outcomes and avoidance of gastrostomy in those referred for G-tube placement.
- We will explore the sensory-motor mechanisms leading to symptoms in infants with GERD. GERD symptoms can be attributed to: a) refluxate properties:

physical (gas, mixed, liquid), chemical (acid, non-acid), spatial (high or low) or temporal (acid or bolus clearance time); or b) luminal clearance mechanisms: esophageal mechano-distention and chemo-sensitive stimulation induced aerodigestive reflexes. The mechanisms for symptoms may underlie in stimulus thresholds, response-frequency, response-latency and response-magnitude of the aerodigestive protective reflexes. Therefore, to test the effects of different treatment strategies on these aerodigestive reflexes, we will interrogate the sensory-motor components before and after proposed therapies.

- Publication history and references pertinent to this proposal are as follows:

## 4.0 Study Endpoints

- Primary Outcome
  - **Clinical outcome of feeding success for those infants transitioning to oral feeds at inception.**
    - The primary endpoint is the feeding success defined as achieving full oral feeds (defined as no need for tube feeds to maintain hydration and nutrition) and/or a  $>/=$  6-point decrease from baseline I-GERQ-R. The time frame is up to 5 weeks after enrollment.
  - **Clinical outcome of feeding success for those infants on full oral feeds at inception.**
    - The primary endpoint is the feeding success defined as maintaining full oral feeds and a  $>/=$  6-point decrease from baseline I-GERQ-R. The time frame is up to 5 weeks after enrollment.
- Secondary Outcomes
  - Clinical Outcomes
    - Length of hospital stay
    - Growth outcomes during the study period and up to 1 year
    - Independent feeding skills over time up to 1 year
    - Respiratory support during the study period and at discharge
    - Developmental outcomes with Bayley's scores at 2 years
    - Individual differences in I-GERQ-R questionnaire
  - Motility Outcomes
    - Mechanisms of aerodigestive clearance and esophageal provocation are evaluated based on esophageal motility studies at inception and after 5 weeks.
  - pH Impedance outcomes
    - 24-hour pH impedance results at inception of study and then 5 weeks later after treatment completed

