## STATISTICAL METHODS

Based on our preliminary data, we had planned to enroll 100 patients (50 per group) to detect 27% or higher increase in proportion of success of study group compared to the conventional group with 80% power and overall one-sided  $\alpha$  level of 0.025. One interim futility analysis was planned at about 50% information prior to the final analysis at 100% information, corresponding to 50 and 100 evaluable patients, respectively. The boundary was determined using Lan-DeMets spending functions to simulate O'Brein-Fleming boundaries(34). Using the target proportion of success, the boundary at the futility analysis was  $p>0.297$ .

Seventy-six infants were randomly assigned till the end of funding for this study and were included in the analysis of demographics and clinical characteristics (**Fig 1, Table 1**) and primary outcome by intent-to-treat. If a patient dropped out before the end of study and no symptom score was evaluable, we treated the patient as a failure for the primary outcome by intention-to-treat. Secondary outcome analysis was performed for 72 subjects (**Fig 1**). Futility boundary was not reached at interim analysis of 50 patients ( $p=0.1 < 0.297$ ) and accrual was continued with DSMB approval. Summary statistics were calculated for patient demographics and clinical characteristics for final analysis. Success rate in achieving PO or reduction in the I-GERQ-R by 6-points was calculated with 95% confidence interval and compared using chi-square test between the conventional and study groups (primary outcomes) for the intention-to-treat and treat-as-treated analyses. Fisher's exact or chi-square test were used to compare other categorical secondary outcomes including feeding method and supplemental oxygen between the groups. Shapiro-Wilk test for normality was used for the continuous outcomes. Paired t-tests or Wilcoxon singed-rank

tests were used to assess changes in growth velocity and feeding therapy characteristics between time-1 and time-2. Two sample t-tests or Wilcoxon rank-sum tests were used to compare these continuous outcomes between conventional and study groups. Median (interquartile range [IQR]), mean (SD), or % was reported, unless stated otherwise.  $P$  values  $<0.05$  were considered statistically significant, and SAS version 9.4 (SAS, Inc, an IBM Company, Chicago, IL) was used.

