## STUDY OUTCOMES

### Primary and Secondary Clinical Outcomes

The clinically meaningful primary and secondary outcomes did not differ significantly between groups (**Table 2**). I-GERQ-R scores for study and conventional groups are shown (**Fig 2**). At inception: positive I-GERQ-R was 19/35 (54%) in the conventional group vs 24/37 (65%) in the study group,  $p=0.36$ . At Time-2: positive I-GERQ-R prevalence was 9/31 (29%) in the conventional group vs 13/34 (38%) in the study group,  $p=0.43$ . In the study group vs conventional group, respectively: a) primary outcome achieved in 33% (95% CI, 19% - 49%) vs 44% (95% CI, 28% - 62%) ( $p=0.28$ ), b) secondary outcomes: independent oral feeding in 65% (95% CI, 48% - 80%) vs 77% (95% CI, 60% - 90%),  $p=0.26$ ,  $\geq 6$ -point I-GERQ-R decrease in 38% (95% CI, 22% - 56%) vs 35% (95% CI, 19% - 55%),  $p=0.82$ , length of stay was 98 [81-132] days vs 108 [83-125] days,  $p=0.89$ , and oxygen requirement at discharge in 19% (95% CI, 8% - 35%) vs 26% (95% CI, 13% - 43%),  $p=0.49$ . There were no significant differences in growth metrics (all  $p>0.05$ ) or developmental scores at 2 years (all  $p>0.05$ ). Feeding outcomes or I-GERQ-R scores did not significantly differ between conventional vs study groups based on feeding method at inception (**Table 3**). Individual I-GERQ-R questions relating to vomiting, regurgitation, and crying (i.e. frequency of emesis, volume of emesis, symptoms with emesis, and crying more than usual in the

past week) had no differences ( $P>0.05$ ) within the group or between the groups across maturation for these individual symptoms, except for symptoms with emesis (never: rarely: sometimes: often: always, %) was 16:16:42:19:6 for conventional group at Time-1 vs 18:18:29:0:35 for study group at Time-1,  $p < 0.01$ .

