**Table 1. Baseline Demographic and Clinical Characteristics of Enrolled Participants**

Variable	Overall Subjects (N = 76)	Conventional Group (N = 36)	Study Group (N = 40)
At Birth			
Gender, Female – n (%)	37 (49)	18 (50)	19 (48)
Race – n (%)			
African American	11 (15)	3 (8)	8 (20)
Asian	1 (1)	0 (0)	1 (3)
Other	6 (8)	2 (6)	4 (10)
Unknown	1 (1)	1 (3)	0 (0)
White	57 (75)	30 (83)	27 (68)
Ethnicity – n (%)			
Hispanic or Latino	2 (3)	2 (6)	0 (0)
Non Hispanic or Latino	71 (93)	32 (89)	39 (98)
Unknown	3 (4)	2 (6)	1 (3)
Gestational Age (GA) – wks	29.3 [27 - 32.9]	29.3 [28 - 32.2]	29.2 [27 - 33.1]
Preterm birth – n (%)	68 (90)	34 (94)	34 (85)
Birth Weight – kg	1.23 [0.9 - 1.9]	1.2 [0.9 - 1.9]	1.3 [0.9 - 2.1]
Size for Gestational Age – n (%)			
Small (< 10th %)	9 (12)	5 (14)	4 (10)
Average (10th - 90th %)	58 (76)	26 (72)	32 (80)
Large (> 90th %)	9 (12)	5 (14)	4 (10)
Cesarean Delivery – n (%)	50 (66)	22 (61)	28 (70)
At Inception			
Postmenstrual age – wks	41.1 (2.5)	41.3 (2.2)	40.9 (2.7)
Chronologic age – wks	10.9 (4.3)	11.1 (4.5)	10.7 (4.3)
Weight – kg	3.5 (0.8)	3.5 (0.8)	3.5 (0.8)
O 2 Requirement at 36 wks PMA – n (%)	36 (47)	17 (47)	19 (48)
O 2 Requirement at 28 days age – n (%)	46 (61)	21 (58)	25 (63)
Feeding Method – n (%)			
Gavage	2 (3)	0 (0)	2 (5)
Transitional	37 (49)	18 (50)	19 (48)
Oral	37 (49)	18 (50)	19 (48)
Nasal Cannula Oxygen – n (%)	23 (30)	11 (31)	12 (30)
Total Intake Volume – mL/kg/day	150 [149 - 154]	150 [148 - 152]	150 [150 - 157]
Total Oral Intake Volume – mL/kg/day	112 [45 - 150]	112 [57 - 150]	112 [22 - 148]
Acid Reflux Index (ARI) – %	9.3 [6.0 - 17.1]	10 [6.0 - 16.7]	9.1 [5.0 - 17.6]
ARI Category – n (%)			
Indeterminate (ARI 3 - 7%)	26 (34)	12 (33)	14 (35)
Abnormal (ARI > 7%)	50 (66)	24 (67)	26 (65)

Data presented as n (%), Median [IQR], or Mean (SD).

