**Table 2. Primary and Secondary Clinical Outcomes and Compliance Measures**

Primary Outcome (intent-to-treat analysis)	Overall (N = 76)	Conventional (N = 36)	Study (N = 40)	P-value
A priori clinical outcome Success, n (%)	29 (38)	16 (44)	13 (33)	0.28
Secondary Outcomes	Overall (N = 72)	Conventional (N = 35)	Study (N = 37)	P-value
I-GERQ-R decrease by 6 – n (%)	24/65 (37)	11/31 (35)	13/34 (38)	0.82
Feeding Outcome at Time 2 – n (%)				0.26
PO	51 (71)	27 (77)	24 (65)	
Transition (PO + Tube)	18 (25)	8 (23)	10 (27)	
Tube	3 (4)	0 (0)	3 (8)	
Length of hospital stay – days	108 [82 - 128]	108 [83 - 125]	98 [81 - 132]	0.89
Hospital stay Inception to Discharge – days	25 [11 - 45]	23 [3 - 39]	27 [16 - 47]	0.26
Weight Growth Velocity (GV) – g/day	27.1 (9.4)	26.5 (7.2)	27.6 (11.1)	0.64
Length GV – cm/day*	0.1 (0.1)	0.1 (0.1)	0.1 (0.1)	0.88
Head Circumference GV – cm/day*	0.1 [0.0 - 0.1]	0.1 [0.0 - 0.1]	0.1 [0.0 - 0.1]	0.87
Feeding Method at Discharge – n (%)				0.32
PO	54 (75)	29 (83)	25 (68)	
Transition (PO + Tube)	14 (19)	5 (14)	9 (24)	
Tube	4 (6)	1 (3)	3 (8)	
Oxygen Requirement at discharge – n (%)	16 (22)	9 (26)	7 (19)	0.49
Compliance to Feeding Methods				
Total Fluid Volume (TFV)				
TFV at Inception- #	N/A	150 [147, 152]	150 [149, 156]	0.8
TFV at Time 2- #	N/A	143 [134, 148]*	133 [126, 137]*	<0.001
# days TFV ≤ 140 / kg / day	N/A	10 [2, 26]	22 [11, 31]	0.005
TFV compliance (TFV <140/kg/d for >75% of time)	N/A	9 (26)	27 (73)	<0.001
Position				
Feeding Position, RSL, %	N/A	5 [1, 17]	78 [12, 94]	<0.001
Feeding in RSL >75% of the time, %	N/A	0 (0)	21 (57)	<0.001
Supine Position Post-Prandial, %	N/A	50 [40, 66]	87 [74, 96]	<0.001
Supine Position Post-prandial >75% of the time, %	N/A	7/34 (21)	27/36 (75)	<0.001
Feeding Duration				
% time feed duration >30 min, %	N/A	4 [0, 37]	15 [0, 69]	0.15
Feeding Duration at Inception, min	N/A	23 [17, 41]	30 [19, 34]	0.64
Feeding Duration at Time 2, min	N/A	23 [18, 28]	26 [20, 30]	0.15
Long-term Follow-up†				
Feeding Method at 6 months – n (%)				0.65
PO	36/50 (72)	21/27 (78)	15/23 (65)	
Transition (PO + Tube)	10/50 (20)	4/27 (15)	6/23 (26)	
Tube	4/50 (8)	2/27 (7)	2/23 (9)	
Feeding Method at 1 year – n (%)				0.11
PO	37/44 (84)	20/22 (91)	17/22 (77)	
Transition (PO + Tube)	4/44 (9)	0/22 (0)	4/22 (18)	
Tube	3/44 (7)	2/22 (9)	1/22 (5)	
CCABSID-III				
Cognitive Score <80 – n (%)	9/44 (21)	5/23 (22)	4/21 (19)	1.00
Cognitive Score – #	95 [90 - 105]	100 [90 - 105]	90 [90 - 100]	0.11

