### 2.2 Hypothesis

- Aim 1
  - The innovative feeding strategy provided over 4 wks is more effective than standard therapy for the acquisition of safe feeding skills by improved symptom scores (Primary), improved individual I-GERQ-R measures, growth measures, reduced lengths of stay and resource utilization (Secondary).
- Aim 2
  - The sensory-motor characteristics of aerodigestive reflexes evoked with induced esophageal stimulation or upon spontaneous esophageal provocation as in GER, improve in the innovative therapy group with regards to: sensory thresholds, response latency and duration, frequency and magnitude of reflexes, TLESRs, spatial-temporal-physical- chemical characteristics of GER events with associated symptom indices.

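### Length of hospital stay has no stated start point, and the figure quoted in the results text is total stay, about 71–79% of which came before inception and could not respond to the intervention

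*Combined protocol and SAP*

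**What the plan says.** Protocol section 4.0 (Study Endpoints) names the secondary outcome only as "Length of hospital stay". It gives no start or end date. Section 2.2 expects the innovative feeding strategy to shorten stay. The report's Outcome Measures section treats length of stay as its economic metric.

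The results text (Primary and Secondary Clinical Outcomes) gives one comparison, study arm first: "length of stay was 98 [81-132] days vs 108 [83-125] days", with p=0.89. Table 2 repeats these figures and adds a second row directly below, "Hospital stay Inception to Discharge – days": 27 [16–47] in the study arm and 23 [3–39] in the conventional arm, p=0.26. The second row is not mentioned in the results text. The abstract names length of stay as a secondary outcome but gives no figure for it. The Discussion says no difference was seen in economic burden measures and gives length of stay as an example.

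For continuous outcomes the Statistical Methods section provides for "Two sample t-tests or Wilcoxon rank-sum" tests between arms. No sample size or power is stated for length of stay.

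**The concern.** Infants were randomised after weeks in hospital, once a qualifying reflux index had been found. Days already spent by then are fixed and cannot respond to feeding volume, position or duration. If they are counted in the endpoint, any effect in days stays the same size while the spread around it grows. The comparison becomes less precise, and the text relies on a number that mostly describes the infants' course before the trial.

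The direction of the numbers matters too. A reader of the text alone sees a median 10 days lower with the bundle. The stay after inception, which is what the bundle could affect, is numerically longer in the study arm, and this appears only in the table. The economic statement, and anyone planning one of the further trials the authors call for, should rest on the component that treatment can change.

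**Working it through.** **Inputs.** From Table 2 (72 infants: 35 conventional, 37 study), median [quartiles] in days:

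| | Overall | Conventional | Study |
|---|---|---|---|
| Total stay | 108 [82–128] | 108 [83–125] | 98 [81–132] |
| Inception to discharge | 25 [11–45] | 23 [3–39] | 27 [16–47] |

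From Table 1, "Chronologic age – wks" at inception (mean, 76 infants): 10.9 overall, 11.1 conventional, 10.7 study. The totals in the results text and Table 2 agree. There is no design figure for this endpoint to reproduce.

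**Step 1. Does total stay include days before inception?** It must, since the two rows differ by about 80 days. As a check, mean age at inception was 10.9 × 7 = 76.3 days, and 76 + 25 = 101, close to 108. This fits most infants having been in hospital since about birth, which is an assumption.

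**Step 2. Share before inception.**
- From medians, 1 − (post-inception / total): overall 1 − 25/108 = 77%; conventional 1 − 23/108 = 79%; study 1 − 27/98 = 72%.
- From age at entry: 76.3/108 = 71%.
- From means approximated as (Q1 + median + Q3)/3: overall 1 − 27/106 = 75%.

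Medians do not subtract exactly, so this is a range of 71–79%, not a single value.

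**Step 3. Noise.** With SD ≈ IQR width / 1.349, the variance ratio is the squared ratio of widths:
- overall: widths 46 and 34, SDs 34.1 and 25.2, ratio (46/34)² = 1.83
- conventional: (42/36)² = 1.36
- study: (51/31)² = 2.71

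Pooling within arms, SD = √[(34·s_c² + 36·s_s²)/70] gives 34.7 days for total stay and 24.8 for post-inception stay, a variance ratio of 1.95. The standard error of the difference, SD × √(1/35 + 1/37), is 8.2 days against 5.9. To illustrate with an assumed 10-day true difference (not a figure from the plan), two-sided 5% power is about 23% for total stay and 40% for post-inception stay.

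**Step 4. Direction, study minus conventional.**

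| | Q1 | Median | Q3 | Approx. mean | p (Table 2) |
|---|---|---|---|---|---|
| Total stay | −2 | −10 | +7 | −1.7 | 0.89 |
| Inception to discharge | +13 | +4 | +8 | +8.3 | 0.26 |

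Interpolating between quartiles, the probability that a study infant stays longer than a conventional infant is about 0.48 for total stay and 0.59 after inception. The corresponding rank-test p-values, about 0.78 and 0.18, do not match the reported ones exactly. Quartiles alone cannot reproduce them.

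**Step 5. Does age at entry explain the difference between the rows?** The arms differ by (10.7 − 11.1) × 7 = −2.8 days in mean age. The median difference moves by 14 days, from −10 to +4. Age imbalance does not by itself account for that.

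**The case against.** The strongest reply is that the post-inception row is already in Table 2, among the secondary outcomes, with both arms and a p-value. The results text cites that table for its statement that outcomes did not differ. No conclusion changes under either definition, no power claim rests on this endpoint, and the abstract quotes no stay figure. All of this stands, and it confines the point to precision and to which figure the text relies on. It does not supply the missing start point in section 4.0 or explain why only total stay is quoted.

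The variance figure is also open to challenge, and fairly. Post-inception stay is bounded at zero and probably skewed, the ratio varies from 1.36 to 2.71 by arm, and a normal-theory multiplier does not carry over directly to a rank test. The direction is plausible, but the size is rough.

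A reader might infer more than the documents support:
- *That the plan counts stay from admission.* Section 4.0 gives no start point. Inclusion of earlier days is inferred from Table 2, and admission cannot be told apart from birth.
- *That earlier days reversed a real effect, or that the bundle lengthened stay.* Neither comparison is significant. The total-stay quartile differences are mixed and its approximate means nearly equal, so there is no clear effect to reverse.
- *That chance imbalance in entry age produced the change of sign.* The 2.8-day difference is too small to do this alone.

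Finally, data were locked in May 2019 and both results are known. Promoting the row with the smaller p-value is a post hoc choice and has to be described as one.

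**Conclusion.** The point holds as one of endpoint definition and precision. The start of the stay is undefined, and about 71–79% of the quoted figure precedes inception. Including those days raises the variance by a factor of about 1.8 overall, with 1.36 to 2.71 as the range by arm. They also obscure the responsive part of the stay, which was numerically longer in the study arm at all three quartiles (27 against 23 days at the median, p=0.26). No harm and no true reversal is shown, and the conclusion of no difference stands.

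This rests on three assumptions: inception is close to randomisation (the interval is not given); SDs can be approximated from interquartile widths; and, for the age check only, infants were in hospital from about birth and the 76 in Table 1 represent the 72 in Table 2. The matter is worth correcting but concerns a secondary endpoint and leaves the trial's main finding untouched.

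**What to change.** In section 4.0, define the secondary endpoint as days from randomisation to discharge. In the results text, report that comparison alongside total stay, base the economic statement on it, and keep total stay as a descriptive figure. State the interval between inception and randomisation, so that readers can see whether the existing Table 2 row is the same quantity or needs recalculation.

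The post-inception figures are already tabulated, so little or no new data work is needed. The cost is a post hoc relabelling of a secondary endpoint. If made after data lock, the change should be labelled as such, with both comparisons shown. A future trial using this design can avoid that cost by fixing the start point in advance.
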